3 STUDY IMPLEMENTATION

3.1 STUDY DESIGN

This is an open label Phase I/II trial, consisting of a safety run-in phase I (Arms 1 and 2) and an expansion phase II, disease-specific cohorts (Arm 3).

In Arm 1 the safety and MTD dose of short term (2 weeks) SX-682 monotherapy lead-in following by treatment with M7824 and CV301 will be determined in participants with solid

tumors (**Schema 1**). An evaluation of DLTs (eDLTs) will occur at the completion of each dose level and will be done prior to enrolling on the next dose level.

In Arm 2 the safety, MTD/RP2D of continuing treatment of SX-682 in combination with M7824 and CV301 will be determined in participants with solid tumors (**Schema 2**). An evaluation of DLTs (eDLTs) will occur at the completion of each dose level and will be done prior to enrolling on the next dose level.

During Arm 3 expansion cohorts, when RP2D of SX-682 in combination with M7824 and CV301 is estimated, we will proceed with enrollment to Cohorts 2 (participants with triple negative breast cancer) and Cohort 3 (participants with HPV negative head and neck cancer) to evaluate efficacy of the SX-682 in combination with M7824 and CV301 (**Schema 3**).

[figure not shown]
SX-682 will be self-administered by the participant orally twice daily according to designated Dose Level (**Table 4**).

Administration of M7824 will be at a flat dose of 1,200 mg every 2 weeks by IV. Participants will receive M7824 treatment every 14 (-1/+3) days.

[figure not shown]
CV301 will be administered at a flat dose for both the prime and booster vaccines. The priming MVA-BN-CV301 is delivered as four subcutaneous injections of 4×10^8 infectious units (Inf.U)/0.5 mL every 14 days for 2 doses (Cycle 1, Day 1 and Cycle 1, Day 15). FPV-CV301 is given subcutaneously at 1×10^9 Inf.U/0.5 mL every 4 weeks starting on Cycle 2 Day 1 x 4 cycles then on Day 1 of every 3 cycles (every 12 weeks) for up to 1 year on trial. Participants will receive CV301 as scheduled (-1/+3) days.

Subjects on all arms will receive combined treatment with study drugs for up to 2 years (BN-CV301 will be administered for up to 1 year on trial; M7824 and SX-682 will be administered for up to 2 years on trial). Furthermore, after 2 years on treatment with M7824 and/or SX-682, the PI can discuss an additional treatment period with CRADA partners as long as in the opinion of the PI the participant continues to gain clinic benefit and is tolerating the drug regimen. Disease progression should be confirmed with a subsequent scan 4 to 8 weeks later prior to removing a participant from study therapy, unless the participant is clinically progressing or is no longer gaining benefit in the opinion of the investigator. Subjects with evidence of disease progression can remain on treatment beyond radiographic progression if in the opinion of the investigator the subject is benefiting from treatment. For complete list of off treatment criteria, see Section **3.7.2**.

Patients may undergo up to three optional biopsies for research purposes only: at baseline, at first restaging (+/- 1 week) and at time of progression.

Schema 1. Cohort 1, Arm 1

Schema 2. Cohort 1, Arm 2. Combination Dose Escalation Cohort.

3.1.1 Dose Limiting Toxicity

Dose-limiting toxicity (DLT) will be defined as any one of the following adverse events (AEs), as defined by CTCAE v5.0, possibly attributable to study drugs by the Investigator, that occur within 28 days after the start of study therapy:

- Any Grade 4 AEs, except for:
 - laboratory values that are determined to not be clinically significant or single laboratory valued that resolve to Grade ≤ 1 or baseline grade within 7 days with adequate medical management.
 - adverse drug reaction which in the opinion of the investigator is not clinically relevant or can be medically managed with minimal risk to the participant (e.g. placement of a pleural catheter for recurrent inflammatory pleural effusions)
- Average QTcf ≥ 501 msec or > 60 msec change from baseline (Grade 3)
- Any Grade 3 AEs except for any of the following:
 - Grade 3 flu-like symptoms or fever, as well as associated symptoms of fatigue, headaches, nausea, emesis which can be controlled with conservative medical management.
 - Tumor flare phenomenon defined as local pain, irritation, or rash localized at sites of known or suspected tumor.

- Any Grade ≥ 3 drug-related amylase or lipase abnormality that is not associated with symptoms or clinical manifestations of pancreatitis.
- Grade 3 Hgb decrease (< 8.0 g/dL) that is clinically manageable with blood transfusions or erythroid growth factor use does not require treatment discontinuation.
- Keratoacanthoma and squamous cell carcinoma of the skin.
- Any endocrinopathy that can be medically managed with hormone replacement
- Grade 3 neutropenia without fever
- Since the safety profile of M7824 is well characterized (see IB), a single grade 3 adverse event known to be associated with M7824, as per IB section 6.2.6 will not be considered a DLT.
 - Additionally, M7824 has a known potential to cause bleeding, with a rate of grade 3 bleeding events as high as 15.3% [92]. Therefore a grade 3 bleeding event will not be considered a DLT.
- Any grade 3 adverse drug reaction which in the opinion of the investigator is not clinically relevant or can be medically managed with minimal risk to the participant (e.g. placement of a pleural catheter for recurrent inflammatory pleural effusions)
- Any grade 3 or higher adverse event or unexpected toxicities due to the combination of therapies that would not be expected with individual agents alone, will be considered a DLT.

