3.1.2 Dose Escalation Common Rules

Starting dose of SX-682 will be 25 mg by mouth twice daily (50 mg total daily dose).

The first 3 participants enrolled on a given dose level of Arms 1 and 2 will be observed for DLT. If no DLT in those 3 participants, the next dose level will open. If DLT(s) occur, see **Table 5**.

There will be an interval of at least 28 days between enrolling the last participant on a given dose level and enrolling a participant on the next dose level in Arms 1 and 2, in order to assess for DLTs.

Subjects who do not complete the DLT observation period for reasons other than a DLT will be replaced and not included in the evaluation.

Participants will be eligible for the DLT evaluation if at least ≥ 85 percent of SX-682 scheduled doses were taken and 100% of scheduled doses of M7824 or CV301 were administered within the DLT period.

In case of DLT, DLT will be documented and participant, per PI discretion, may continue study treatment if toxicity could be managed by interruption of the dose of study treatment or dose reductions (See section **3.4**). Participant, once having DLT, will not be used for DLT evaluation on another dose level if treated on a lower dose level.

Any of the trial drugs may be discontinued for toxicity per the discretion of the primary investigator if it is felt that the toxicity can be directly linked to a specific drug or drugs. Per PI

discretion participant can continue treatment with 2 other drugs. However, if 2 drugs or more must be discontinued, the participant will be taken off treatment.

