3.2 STUDY STOPPING RULES

For safety reasons, enrollment will be temporarily halted until an expedited safety report has been evaluated by the investigators, IND sponsor, and submitted to the FDA for either of the following events attributable to treatment regimen occurring within 30 days of receiving investigational agent:

- One occurrence of grade 5 toxicity
- Two occurrences of grade 4 toxicity
- Grade 3 or higher toxicities that occur at a higher rate than expected for each individual agent in the combination.

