3.4.4.1 Adverse Drug Reactions (ADRs) Requiring Treatment Discontinuation

All adverse events in this trial will be graded using the NCI Common Terminology Criteria for Adverse Events (CTCAE) version 5.0.

Any Grade 4 ADRs require permanent treatment discontinuation except for any of the following:

- Single laboratory values out of normal range that do not have any clinical correlate and resolve to Grade ≤ 1 or Baseline grade within 7 days with adequate medical management.
- Grade 4 symptomatic endocrinopathies (e.g., thyroiditis or hypophysitis), treatment should be delayed, and treatment started according to best medical judgement based on the most updated professional guidelines (NCCN, EMSO, SITC, etc.). Following the initiation of appropriate medical therapy for the endocrinopathy, treatment can be resumed per PI discretion.

- Asymptomatic lab abnormalities (Grade 3 or 4) as described below in the Grade 3 ADR section.
- Grade 4 non-tumor bleeding will not require permanent treatment discontinuation if an alternative explanation for the bleeding is identified. If no alternative explanation is identified, treatment must be permanently discontinued.

Any Grade 3 ADRs require treatment temporary discontinuation except for any of the following:

- Transient (\leq 48 hours) Grade 3 flu-like symptoms or fever, which is controlled with medical management.
- Transient (\leq 48 hours) Grade 3 fatigue, local reactions, headache, nausea, emesis that is controlled with medical management.
- Tumor flare phenomenon defined as local pain, irritation, or rash localized at sites of known or suspected tumor.
- Any single Grade \geq 3 drug-related transaminase, alkaline phosphatase, or bilirubin abnormality with no other associated laboratory (or other) abnormality that is not associated with symptoms or clinical manifestations of hepatitis. If the liver function abnormality not associated with symptoms or clinical manifestations of hepatitis has not resolved to Grade \leq 1 within the subsequent 2 cycles (56 days), the subject should permanently discontinue treatment with M7824.

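### An attributable death in the DLT window counts as a DLT only if it is an unexpected combination effect; other such deaths can drop out of the 3+3 count

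*Combined protocol and SAP*

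**What the plan says.** Section 3.1.1 limits DLTs to CTCAE v5.0 events "possibly attributable to study drugs by the Investigator, that occur within 28 days after the start of study therapy". An event must then meet one of four criteria:

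- "Any Grade 4 AEs, except for" certain laboratory values and certain reactions judged by the investigator;
- a QTcF criterion;
- "Any Grade 3 AEs except for any of the following", followed by a list that includes grade 3 bleeding, on the ground that bleeding is a known M7824 risk;
- "Any grade 3 or higher adverse event or unexpected toxicities due to the combination of therapies that would not be expected with individual agents alone".

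Section 3.1.2 adds two rules on who is counted. The first is replacement: "Subjects who do not complete the DLT observation period for reasons other than a DLT will be replaced and not included in the evaluation". The second makes a participant evaluable for DLT only with at least 85% of scheduled SX-682 doses and 100% of scheduled M7824 or CV301 doses in the DLT period. Section 10.3.1 repeats the second rule. Neither place makes an exception for a participant who has a DLT or dies.

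Section 3.2 temporarily halts enrollment for, among other events attributable to the regimen within 30 days, "One occurrence of grade 5 toxicity". Section 7.5.2 has the DSMB meet when halting criteria are met. Neither section mentions the DLT count.

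**The concern.** Determining the MTD (Arm 1) and the RP2D (Arm 2) are primary objectives, and both rest on the Table 5 count. So does the gate in Sections 3.1.3 and 3.1.4, which asks whether Arm 1 levels 1 to 3 produced 0 DLTs or at least 1.

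If the definition misses some attributable deaths, the replacement rule does more than leave them unclassified. It takes those participants out of both numerator and denominator. The most severe outcome would then be treated like a withdrawal for administrative reasons, and the escalation table would be applied to the participants who remain.

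**Working it through.** **1. The plan's own figures.** Section 10.2 reproduces: 3 × 3 = 9 as the minimum for Arm 1, 3 × 6 = 18 as the maximum for its first three levels, 5 × 6 = 30 per arm, and 30 + 30 = 60 for phase I. The plan gives no probability of escalation to check.

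**2. Which attributable deaths meet a DLT criterion?**

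| Death in the window | Grade 4 bullet | Grade 3 bullet | Last bullet |
|---|---|---|---|
| From SX-682 alone, in the two-week lead-in | No, it is grade 5 | No | No, no combination has been given |
| From a known risk of one agent, e.g. M7824 bleeding | No | No | Arguably no, since it is expected with that agent |
| From an unexpected effect of the combination | No | No | Yes |

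Taking the first SX-682 dose as the start of study therapy, the lead-in (Days -14L to -1L) fills 14 of the 28 days. In Arm 1, SX-682 stops before M7824 and CV301 start, so attribution to the combination is harder there as well.

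**3. What happens to a participant in the first two rows?** The window was not completed and the reason was not a DLT, so Section 3.1.2 replaces them. The dose-percentage rule points the same way: someone who dies in the lead-in has received no M7824 or CV301.

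**4. Effect on Table 5 of one such death**, if the replacement completes the window without a DLT:

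| Situation | Death counted | Death replaced |
|---|---|---|
| No other DLT in the first 3 | 1 of 3: expand to 6 | 0 of 3: next level |
| One other DLT in the first 3 | 2 of 3: stop | 1 of 3: expand to 6 |
| One DLT in the first 3, death in the second 3 | 2 of 6: stop | 1 of 6: next level |

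In Table 4 each level doubles the SX-682 dose of the one below.

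**5. Effect on the Arm 1 gate.** If the death is the only event in levels 1 to 3 and is not counted, Arm 2 opens at level 2 (100 mg/day). If it is counted, Arm 1 continues to level 4 (400 mg/day) and level 5 (800 mg/day), and Arm 2 later starts at level 1 (50 mg/day).

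**6. Size, under assumed rates.** For a true DLT probability p, the 3+3 rule passes a level with probability

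P(p) = (1 − p)³ + 3p(1 − p)² × (1 − p)³ = (1 − p)³ + 3p(1 − p)⁵.

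Let d be the rate of other DLTs and f the rate of attributable deaths that miss every bullet. With deaths counted, p = d + f. With deaths replaced, p = d/(1 − f). For d = f = 0.10:

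- counted, p = 0.20: 0.512 + 0.6 × 0.32768 = 0.709;
- replaced, p = 0.10/0.90 = 0.111: 0.702 + 0.185 = 0.887.

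| d | f | Counted | Replaced | Difference |
|---|---|---|---|---|
| 0.10 | 0.01 | 0.889 | 0.904 | 0.015 |
| 0.05 | 0.05 | 0.906 | 0.971 | 0.065 |
| 0.10 | 0.10 | 0.709 | 0.887 | 0.178 |
| 0.10 | 0.20 | 0.494 | 0.862 | 0.368 |
| 0.20 | 0.20 | 0.309 | 0.600 | 0.291 |

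The documents give neither d nor f. The calculation treats participants as independent and ignores any change made after the Section 3.2 halt.

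**The case against.** **A death would not pass unnoticed.** One attributable grade 5 event halts enrollment until a safety report has been evaluated and sent to the FDA. The DSMB meets and can recommend modifying or terminating the trial, and Section 7.5.1 bases escalation on toxicity data from earlier participants. This stands: silent escalation after a death is implausible, and the authors probably intend deaths to count. It does not repair the count, because no section says how the death is entered when enrollment resumes.

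**The wording may already cover deaths.** One could read any grade 4 as grade 4 or worse. But Section 3.2 lists grades 4 and 5 separately, and Section 3.1.1 says when it means a grade or higher. One could also split the last bullet so that every event of grade 3 or higher is a DLT, but that would empty all the listed exclusions. Whether a fatal bleed counts as expected with M7824 is open to argument. A death in the SX-682-only lead-in is the clearer case.

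**Stronger readings that a reader might infer.** The documents do not support these:

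- *No death can be a DLT.* The last bullet reaches grade 5 for unexpected combination effects.
- *The grade 4 exception causes the gap.* That exception, for an "adverse drug reaction which in the opinion of the investigator is not clinically relevant or can be medically managed with minimal risk to the participant", concerns grade 4 events. A fatal event cannot sensibly be called manageable with minimal risk.
- *The gap always pushes the dose upward.* Within an arm it favors escalation. At the Arm 1 level 3 gate, not counting the death opens Arm 2 at level 2, while counting it sends Arm 1 on to levels 4 and 5.
- *Some overall chance of a miscounted death can be quoted for up to 60 participants.* No death rate is given, 60 is a ceiling, and such a figure would include deaths that the last bullet does count.

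**Conclusion.** The point holds as a gap in definition with a real effect on a primary objective. Read literally, Sections 3.1.1 and 3.1.2 leave some attributable deaths out of the 3+3 count, and Sections 3.2 and 7.5.2 ensure review without putting them back. A single such death is enough to change a Table 5 decision or the branch taken at the Arm 1 gate. That conclusion needs no assumed rate.

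The average effect does depend on assumptions. It is small if such deaths are rare: 0.015 per level at 10% other DLTs and 1% uncounted deaths. It is about 0.07 to 0.37 per level when both rates lie between 5% and 20%.

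A separate and lesser point is that the investigator-opinion exception for grade 4 reactions in Section 3.1.1 has no direct counterpart in Section 3.4.4.1: "Any Grade 4 ADRs require permanent treatment discontinuation except for any of the following". A reader might call this a contradiction, but the documents do not establish one. Section 3.4.4.1 sits under M7824 and governs discontinuation rather than DLTs. SX-682 has its own rule in Section 3.4.2, and Section 3.1.2 lets a participant with a DLT stay on treatment. It is a consistency check for the sponsor, and this review does not say which rule should govern.

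**What to change.** Reconcile Sections 3.1.1, 3.1.2, 3.2 and 10.3.1 so that they state together:

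- that an attributable grade 5 event in the DLT window is entered in the Table 5 count, and in the total used at the Arm 1 gate, whether or not it is a combination effect;
- that a participant with such an event is not removed by the replacement rule or the dose-percentage rule;
- how an event that triggers the Section 3.2 halt is carried into the count when enrollment resumes.

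Separately, check the grade 4 exception in Section 3.1.1 against Section 3.4.4.1 and state whether the difference is intended.

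The cost is wording in four sections, with no new procedures and no change to the planned sample size. The downside is that escalation may be slightly slower, because a level with such a death would be expanded or stopped instead of passed.

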3.1.3 Sequential Dose Escalation (Arm 1)

In Arm 1 participants will receive SX-682 as monotherapy for 2 weeks during the lead-in (Days -14L to -1L) and then continue treatment with M7824 and CV301 starting Cycle 1, Day 1.

The dose escalation will start from dose level 1 and continue until dose level 3 (**Table 4**) in sequential order using a standard 3+3 design (**Table 5**). Aside from looking at DLTs within a given dose level, the total number of DLTs will also be evaluated among the initial 3DLs in Arm 1 to guide further safety assessments. If there are 0 DLTs reported in the initial 3 DLs (minimum of 12 participants) in Arm 1, then Arm 2 can open as depicted in Schema 2 with starting at DL2. If there is 1 or more DLTs identified among all the participants in the first 3 DLs, enrollment in Arm 1 will continue with the next participants being enrolled on DL4 then DL5, using a 3+3 design in order to determine the maximally tolerated dose (MTD) before proceeding to Arm 2, DL 1.

Dose escalation will proceed in groups of 3–6 participants. The MTD is the dose level at which no more than 1 of up to 6 participants experience DLT during 28 days of treatment, and the dose below that at which at least 2 (of ≤ 6) participants have DLT as a result of the drug.

Table 4: Dose levels of SX-682

Dose Escalation Schedule		
Dose Level	Dose of SX-682	Total SX-682 daily dose
Level 1	25 mg by mouth twice daily	50 mg
Level 2	50 mg by mouth twice daily	100 mg
Level 3	100 mg by mouth twice daily	200 mg
Level 4	200 mg by mouth twice daily	400 mg
Level 5	400 mg by mouth twice daily	800 mg

SX-682 is dispensed as a 25mg tablet. M7824 and CV301 will be given at fixed doses.

Table 5. Escalation Decision Rules

Number of Participants with DLT at a Given Dose Level	Escalation Decision Rule*
0 out of 3	Enter up to 3 participants at the next dose level
≥ 2	Dose escalation will be stopped. This dose level will be declared the maximally administered dose (highest dose administered). Up to three (3) additional participants will be entered at the next lowest dose level if only 3 participants were treated previously at that dose.

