3.1.4 Combination Dose Escalation (Arm 2)

In Arm 2 participants will receive SX-682 as monotherapy for the lead-in (Days -14L to -1L) and then will continue treatment with SX-682 combined with M7824 and CV301 starting on Cycle 1 Day 1.

If 6 participants have been treated in Arm 1 at dose level 3 without DLT during DLT period, the dose escalation of SX-682 will start from dose level 2 and continue until dose level 5 ([Table 4](#)) in sequential order using a standard 3+3 design ([Table 5](#)).

If there was 1 or more DLT in Arm 1 at dose level 1 through 3 during DLT period, the dose escalation of SX-682 will start from dose level 1 and continue until dose level 5 ([Table 4](#)) in sequential order using a standard 3+3 design ([Table 5](#)).

If in Arm 1 dose level 1 or 2 are estimated as MTD, we will submit an amendment with justification for study continuation.

[figure not shown]
Dose escalation will proceed in groups of 3–6 participants. The MTD is the dose level at which no more than 1 of up to 6 participants experience DLT during 28 days of treatment, and the dose below that at which at least 2 (of ≤ 6) participants have DLT as a result of the drug. The RP2D may not necessarily be the same as the MTD.

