3.4.2 SX-682

If any SX-682 related AE observed is grade > 2 (except for electrolyte abnormalities that can be easily replenished or other lab abnormalities that have no clinical consequence or can be easily medically managed with minimal risk to the participant), treatment should be delayed by 1 week (except for hyperbilirubinemia where drug will be held for grade 2) – and up to 4 consecutive weeks. If, with a delay of up to 4 weeks, the treatment related AE resolves, then SX-682 can be resumed at the same dose level or at a lower dose level per the PI discretion.

If, after 4 weeks of delay, all treatment related AEs have still not resolved (to grade ≤ 1), then any further treatment with SX-682 should be delayed until AEs are resolved (to grade ≤ 1), and then reduced by one dose level at the time of reinitiating.

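### The grade 3 bleeding exemption from the DLT definition rests on M7824 but has no onset condition, so as written it also covers the 14-day lead-in on SX-682 alone

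*Combined protocol and SAP*

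**What the plan says.** Section 3.1.1 defines a DLT as one of a list of adverse events "possibly attributable to study drugs by the Investigator, that occur within 28 days after the start of study therapy". Grade 3 events count unless they are on a list of exceptions. Two exceptions are argued from M7824. The first says that "a single grade 3 adverse event known to be associated with M7824, as per IB section 6.2.6 will not be considered a DLT". Nested beneath it, a second cites grade 3 bleeding rates with M7824 of up to 15.3% and concludes: "Therefore a grade 3 bleeding event will not be considered a DLT". Neither refers to date of onset or to prior M7824 exposure.

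Sections 3.1.3 and 3.1.4 give two weeks of SX-682 alone (Days -14L to -1L) in both escalation arms, and M7824 starts on Cycle 1 Day 1. Table 4 escalates SX-682 only. Table 5 decides escalation on the DLT count at each level. Section 3.1.3 adds a gate across levels: "If there are 0 DLTs reported in the initial 3 DLs (minimum of 12 participants) in Arm 1, then Arm 2 can open", starting at DL2. With one or more DLTs in DL1-3, Arm 1 goes on to DL4 and DL5, and Arm 2 then starts at DL1.

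**The concern.** The reason for the exemption is that a known M7824 toxicity should not be charged to the SX-682 dose. That reason cannot apply before M7824 is given. During the lead-in, SX-682 is the only study drug to which a bleed could be attributed. SX-682 is also the only drug being escalated, and its single-agent safety is a primary objective of Arm 1. In Arm 1 the lead-in is the whole of a participant's SX-682 exposure.

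At stake are the two decisions that run on DLT counts. For Table 5, the omission can only lower the count, so a level becomes more likely to pass. For the Arm 1 gate, the omission can change both where Arm 2 starts and whether Arm 1 goes on to 200 and 400 mg twice daily.

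**Working it through.** The plan gives no figure for this point, so the check is first one of text against schedule and then an illustration on assumed rates.

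**Is the lead-in inside the DLT window?** The window is 28 days from the start of study therapy. Section 3.1.2 makes a participant evaluable only if at least "85 percent of SX-682 scheduled doses were taken and 100% of scheduled doses of M7824 or CV301 were administered within the DLT period". Footnote 3 of the study calendar (section 3.5) gives SX-682 in Arm 1 during the lead-in only, so the SX-682 condition has meaning in Arm 1 only if the DLT period includes the lead-in. Section 10.3.1 also counts toxicity from the first SX-682 dose. The lead-in is therefore 14/28 = 50% of the window. If the window were instead read as starting at C1D1, a lead-in bleed would still go uncounted, because it would precede the window.

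**Does another clause restore the event?** The last item of 3.1.1 makes toxicity due to the combination a DLT. An event on monotherapy cannot meet it.

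**What happens to the participant?** Section 3.4.2 says that for an SX-682-related event above grade 2, with some exceptions, "treatment should be delayed by 1 week". Assume that held doses still count as scheduled.
- Arm 2: 28 days × 2 = 56 doses. A one-week hold loses 14, and 42/56 = 75%, below 85%, so the participant is replaced.
- Arm 1: 14 days × 2 = 28 doses. A full week's hold leaves 14/28 = 50%, so the participant is replaced. A bleed after day 12 leaves at least 24/28 = 85.7%, so the participant stays evaluable on this criterion and counts as a non-DLT.

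In neither case does Table 5 record a DLT.

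**Table 5.** A level passes with 0 of 3 DLTs, or 1 of 3 followed by 0 of 3:

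P(pass) = (1−p)³ + 3p(1−p)⁵.

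Let r = 10% be the assumed rate of other DLTs, and q the assumed rate of exempted lead-in bleeds, independent of r.
- Current text, participant kept: p = r = 0.10, so 0.729 + 0.3 × 0.590 = 0.906.
- Event counted: p = 1 − (1−r)(1−q).
- Current text, participant replaced: p = r / [1 − q(1−r)].

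| q | Event counted: p, P(pass) | Kept as non-DLT: P(pass) | Replaced: p, P(pass) |
|---|---|---|---|
| 1% | 0.109, 0.89 | 0.91 | 0.101, 0.90 |
| 2% | 0.118, 0.88 | 0.91 | 0.102, 0.90 |
| 5% | 0.145, 0.82 | 0.91 | 0.105, 0.90 |

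**Arm 1 gate.** The route changes if there is no other DLT but at least one exempted bleed among n participants:

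P(change) = (1−r)ⁿ × [1 − (1−q)ⁿ].

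With n = 12 and r = 10%, (0.9)¹² = 0.282:
- q = 1%: 0.282 × (1 − 0.886) = 0.03
- q = 2%: 0.282 × (1 − 0.785) = 0.06
- q = 5%: 0.282 × (1 − 0.540) = 0.13

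With n = 9, the lower figure in section 10.2, the results are 0.03, 0.06 and 0.14. With n = 12 they are 0.06, 0.12 and 0.25 if r = 5%, and 0.01, 0.01 and 0.03 if r = 20%.

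**The case against.** The strongest objection is about context. The bleeding sentence is nested under an exemption for events associated with M7824, opens with M7824's bleeding potential, and concludes from it. A careful investigator could take it to mean M7824-associated bleeding, which excludes anyone who has not had M7824. That is plausible as intent. But the operative sentence does not say so, and if it is the intent, the fix only writes it down.

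Second, few events qualify. The bleed must be grade 3 (grade 4 stays under the grade 4 rule), fall within 14 days, be possibly due to SX-682, and not be judged manageable with minimal risk, which is exempt for any drug. Section 2.1.2 excludes bleeding diathesis and recent clinically significant bleeding. Section 3.4.4.4.2 names SX-682 for anemia but explains mucosal bleeding through M7824. This stands, and it limits the size.

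Third, section 3.4.4.1 requires permanent discontinuation after grade 3 non-tumor bleeding that needs intervention or hospitalization, unless another explanation is found. It sits under M7824, so its reach into the lead-in is unclear. If it applies, replacement is more likely, and the smaller differences in the table are the relevant ones.

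Fourth, other controls see the event: the halting rule (3.2), weekly toxicity review (7.5.1), DSMB review (7.5.2), mucosal-bleeding AESI records (8.1.6) and separate monotherapy evaluation (10.4.2). The RP2D also need not equal the MTD (3.1.4). These limit the consequence, but none adds the event to the DLT count.

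**Conclusion.** The point holds as a gap between a stated rule and the dosing schedule. As written, 3.1.1 leaves out of the DLT count a possible toxicity of the only escalated drug, on the ground of a drug not yet given. It should be fixed, but the effect is probably small. On the assumed rates, counting the event lowers the chance of passing a level from 0.91 to 0.89, 0.88 or 0.82 (from about 0.90 if the participant would have been replaced), and the gate route changes with probability 0.03, 0.06 or 0.13. These rest on assumed q and r, independence, and, for the gate, 12 participants. Section 1.2 and the Investigator's Brochure were not available for this check, so the SX-682 bleeding rate is unknown here, and so is how much the companion exemption adds.

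Three stronger readings are not supported:
- A reader might infer a large effect. At a true DLT rate of 1/3, exempting half of all DLTs would raise the chance of passing from 0.43 to 0.78. But that implies lead-in grade 3 bleeding due to SX-682 in 1/3 × 1/2 = 16.7% of participants, above the 15.3% quoted for M7824 itself.
- A reader might infer that the omission always works against safety. At the gate the direction is mixed: an uncounted bleed starts Arm 2 at DL2 instead of DL1, while a counted one sends Arm 1 on to DL4-5.
- A reader might infer that the event goes unseen. It is recorded and reviewed, but not counted as a DLT.

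Nothing here questions the exemption for bleeding after C1D1.

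**What to change.** Add to both M7824-based exemptions in 3.1.1: *only for events with onset on or after the first M7824 dose (C1D1)*. Lead-in events then fall under the general grade 3 rule and its other exceptions, and the purpose of the exemption is kept. Date of onset is already collected (section 8.2), and section 10.4.2 needs no change.

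The cost is that a few more events may count as DLTs. On the zero-DLT path, phase I needs up to 12 in Arm 1 plus 4 × 6 = 24 in Arm 2 (DL2-5), or 36. One counted DLT at each of DL1 and DL2 adds 2 × 3 = 6 there, 2 × 6 = 12 at Arm 1 DL4-5, and 6 at Arm 2 DL1. That is 24 more, giving 60, which equals but does not exceed the planned maximum in section 10.2.
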